6.5.2 Vital signs

Vital signs will be performed at visits specified in the table of assessments ([Table 6-1](#)). Measurements will include systolic and diastolic blood pressure, pulse rate, and body temperature.

6.5.3 Height and weight

Height in centimeters (cm) will be measured at the visits specified in the table of assessments (See [Table 6-1](#)).

Body weight (to the nearest 0.1 kilogram [kg] in indoor clothing, but without shoes) will be measured at the visits specified in the table of assessments (See [Table 6-1](#)).

Body Mass Index (BMI) will be calculated as the weight in kg divided by the height in meters squared.

6.5.4 Laboratory evaluations

A central laboratory will be used for analysis of all specimens detailed in this section. Details on the collections, shipment of samples and reporting of results by the central laboratory are provided to investigators in the laboratory manual.

Clinically notable laboratory findings are defined in [Appendix 1](#).

6.5.4.1 Hematology

Hemoglobin, hematocrit, red blood cell count, white blood cell count with differential, and platelet count will be measured according to the assessment schedule in [Table 6-1](#). Other reflex testing will be performed as outlined in the laboratory manual.

6.5.4.2 Clinical chemistry

BUN/urea, creatinine, creatine kinase, total bilirubin, AST, ALT, alkaline phosphatase, gamma-glutamyl transpeptidase, lactate dehydrogenase, sodium, potassium, chloride, calcium, magnesium, iron, bicarbonate, cholesterol, triglycerides, high-sensitivity C-reactive protein, phosphorus, total protein, albumin, glucose, uric acid, amylase, lipase, CK-MB and Troponin-I (in response to CK results outside of the normal range), HbA1c (collected at Visit 1 only) (■■■■ RAST/ImmunoCAP test), will be measured according to the assessment schedule (Table 6-1). Other reflex testing will be performed as outlined in the laboratory manual.

If the total bilirubin concentration is increased above 1.5 times the upper limit of normal range, the total bilirubin will be differentiated into the direct and indirect reacting bilirubin.

All patients with laboratory tests containing clinically significant abnormalities must be followed until the values return to within the normal ranges or until a clinical explanation is identified, even after study drug has discontinued.

6.5.4.3 Urinalysis

Urine for urinalysis and urine chemistry will be collected according to the collection schedule in Table 6-1. **All samples for urinalysis and urine chemistry will be sent to the central laboratory for analysis.** The urinalysis evaluation by the central laboratory will include a urine dipstick for specific gravity, protein, glucose, leukocytes and blood and, if required, a microscopic examination. Urine chemistry and microscopic examination of the urine will be performed by the central laboratory as delineated in Table 15-1 “Specific Renal Alert Criteria and Actions” in Section 7.4 “Renal Safety Monitoring” of this protocol. Other reflex testing will be performed as outlined in the laboratory manual.

6.5.5 Electrocardiogram (ECG)

ECGs will be measured according to the assessment schedule in Table 6-1. At Visit 1, an ECG will be measured to test for eligibility for trial inclusion.

ECGs must be recorded according to the ECG investigator manual in the supine position to ensure a stable baseline. The preferred sequence of cardiovascular data collection during study visits is PRO collection first, followed by ECG, and then other study procedures (see Section 6). The Fridericia QT correction formula (QTcF) must be used for clinical decisions.

Single 12 lead ECGs are to be collected with ECG machines supplied by the core laboratory. Full details of all procedures relating to the ECG collection and reporting will be contained in an investigator manual to be provided to each investigator site.

The original trace will be sent electronically for central review directly from the ECG machine. Two ‘identical’ duplicate print-outs will be generated and kept at the investigator site as source documentation and as back-up for submission to the central laboratory in case of problems with the electronic transmission. Each page of the ECG tracing must be labeled with study number (CQAW039A2317), subject initials (where this is allowed according to local regulations), subject number, date and time, and filed in the study site source documents.

For any ECGs with subject safety concerns, two additional ECGs must be performed to confirm the safety finding and copies forwarded to the central ECG laboratory for assessment. Clinically significant ECG findings prior to dosing with study drug must be discussed with the Novartis responsible person or designee.

Clinically significant abnormalities must be recorded on the relevant section of the medical history/Current medical conditions/AE CRF / e(CRF) page as appropriate.

In the event that the central cardiologist reports that an ECG is abnormal, then the investigator must comment as to whether the ECG abnormality is either clinically significant or clinically insignificant. If necessary a cardiologist may be consulted.

6.5.6 Pregnancy and assessments of fertility

All women and adolescent girls of child bearing potential will have serum pregnancy test according to the assessment schedule in [Table 6-1](#). Pregnancy testing will begin at the visit a patient is first identified as being of child bearing potential.

A positive urine pregnancy test requires immediate interruption of study drug until serum β -hCG is performed and found to be negative. If positive, the patient must be discontinued from study drug and the patient is followed to understand the outcome of the pregnancy.

6.5.7 Appropriateness of safety measurements

The safety assessments selected are standard for this indication/patient population.

6.6 Other assessments

In addition to patient reported outcomes at the visits indicated in [Table 6-1](#), [REDACTED]

6.6.1 Clinical Outcome Assessments (COAs)

6.6.1.1 Patient Reported Outcomes (PRO)

The impact of QAW039 on various aspects of patient's health status will be assessed by the following measures:

- Asthma Control Questionnaire-5 (ACQ-5) to assess improvement in asthma symptom control;
- Asthma Quality of Life Questionnaire+12 (AQLQ+12) to measure health-related quality of life (HRQOL); and

[REDACTED]

All questionnaires will be completed in the language most familiar to the respondent, at the scheduled study visit prior to the patient seeing the investigator for any clinical assessment or evaluation. The patient must be given sufficient instruction, space, time and privacy to complete the questionnaire. The study coordinator must check the responses to the questionnaire for completeness and encourage the patient to complete any missing responses.

Available training materials related to the administrative procedures of the questionnaires will be provided to the sites.

All patients will complete the PRO questions via a handheld electronic device or an electronic tablet. Patients must be given sufficient space and time to complete all study PROs. If patients experience any difficulties with submission after they complete the PROs, the study staff must assist them with submitting their PRO responses. Attempts must be made to collect responses to all PROs for all patients, including from those who prematurely discontinue prior to the study evaluation completion visit, however, if patients refuse to complete PROs, this must be documented in study source records. Patient's refusal to complete study PROs are not protocol deviations.

Completed questionnaires will be reviewed and examined by the investigator, before the clinical examination, for responses that may indicate potential adverse events (AEs) or serious adverse events (SAEs). The investigator must review not only the responses to the questions in the questionnaires but also for any unsolicited comments written by the patient. If AEs or SAEs are confirmed, then the physician must record the events as per instructions given in [Section 7.1](#) and [Section 7.2](#) of the protocol.

The PROs ACQ-5, AQLQ+12, [REDACTED] questionnaires should always be completed before any other assessments and in the following order when done at the same visits (see [Section 6](#)):

- ACQ-5
- AQLQ+12

■ [REDACTED]

Asthma Control Questionnaire (ACQ-5)

In this study, the ACQ-5 will be used to assess improvements in asthma symptom control.

The original ACQ consists of 7 items: 5 items on symptom assessment, 1 item on rescue bronchodilator use, and 1 item on airway caliber (% FEV₁ predicted). The rescue bronchodilator use and % FEV₁ predicted items are not included in the ACQ-5. The ACQ was originally validated in patients with asthma over aged 17 years ([Juniper et al 1999](#), [Juniper et al 2006](#)), and is one of several asthma control measures recommended by the GINA Guidelines. The ACQ has been fully validated, including patients aged from 6 to 16 years ([Juniper et al 2010](#)) and including a minimal important difference (MID) or smallest change that can be considered clinically important (0.5).

The ACQ-5 will be self-administered at the clinic and only takes a few minutes to complete. Patients will be asked to recall how their asthma has been during the previous week and to respond to the symptom questions on a 7-point scale (0=no impairment, 6=maximum impairment). The questions are equally weighted and the ACQ-5 score is the mean of the 5 questions: therefore, between 0 (totally controlled) and 6 (severely uncontrolled) ([Juniper et al 1999](#); [Juniper et al 2005](#); [Juniper et al 2006](#)).

The ACQ will be collected in an electronic format. The ACQ will be completed by patients at the visits specified in the table of assessments (See [Table 6-1](#)). The questionnaire must be completed before the AQLQ+12 and before any other assessments (see [Section 6](#)). The appropriate language version(s) of the questionnaire will be used in each participating country. The same language version of the questionnaire must be used by a particular patient throughout the study.

The study coordinator must be familiar with the instrument and the associated user guides and training materials provided. Patients must complete the questionnaire in a quiet area and are allowed to ask questions; however the site staff must take care not to influence the patient's response. In response to a question, patients must be instructed to provide the truest or best response for them.

Asthma Quality of Life Questionnaire for 12 years and older (AQLQ+12)

In this study, the disease-specific AQLQ+12 will be used to measure health-related quality of life in patients. The measure was originally validated for use in patients with asthma aged "12 to 80 years ([Juniper et al 2005](#))".

[figure not shown]
The AQLQ+12 comprises a total of 32 individual questions that span a total of four domains: symptoms, activity limitation, emotional function, and environmental stimuli. Test-retest reliability, construct validity (cross-sectional and longitudinal), and responsiveness have been demonstrated (see [Appendix 8](#)).

[figure not shown]
The AQLQ+12 will be self-administered at the clinic. It takes about 4 to 5 minutes to complete. Patients are asked to recall their experiences during the previous 2 weeks and to score each item on a 7-point scale (7 = not at all impaired to 1 = severely impaired). The AQLQ+12 yields individual domain scores, which is the mean of all items in each domain, and an overall score, which is the mean of all 32 individual responses. Higher scores indicate less impairment in HRQOL.

The AQLQ+12 will be collected in an electronic format. The questionnaire will be completed by patients at the visits specified in the table of assessments (See [Table 6-1](#)).

The appropriate language version(s) of the questionnaire will be used in each participating country. The same language version of the questionnaire must be used by a particular patient throughout the study.

The study coordinator must be familiar with the instrument and the associated user guides and training materials provided. The patient must complete the questionnaire in a quiet area and be allowed to ask questions; however site staff must take care not to influence the patient's responses. The patient will be instructed to provide the truest and for them best response.

7 Safety monitoring

7.1 Adverse events

An adverse event (AE) is any untoward medical occurrence (e.g., any unfavorable and unintended sign [including abnormal laboratory findings], symptom or disease) in a subject or clinical investigation subject *after providing written informed consent* for participation in the study until the end of study visit. Therefore, an AE may or may not be temporally or causally associated with the use of a medicinal (investigational) product.

In addition, all reports of intentional misuse and abuse of the product are also considered an adverse event irrespective if a clinical event has occurred.

The occurrence of adverse events must be sought by non-directive questioning of the patient at each visit during the study. Adverse events also may be detected when they are volunteered by the patient during or between visits or through physical examination findings, laboratory test findings, or other assessments.

Abnormal laboratory values or test results constitute adverse events only if they fulfill at least one of the following criteria:

- they induce clinical signs or symptoms,
- they are considered clinically significant,
- they require therapy.

Clinically significant abnormal laboratory values or test results must be identified through a review of values outside of normal ranges/clinically notable ranges, significant changes from baseline or the previous visit, or values which are considered to be non-typical in patient with underlying disease. Investigators have the responsibility for managing the safety of individual patient and identifying adverse events. Alert ranges for laboratory and other test abnormalities are included in [Appendix 1](#).

Adverse events must be recorded in the Adverse Events CRF under the signs, symptoms or diagnosis associated with them, accompanied by the following information:

- The severity grade:
 - mild: usually transient in nature and generally not interfering with normal activities
 - moderate: sufficiently discomforting to interfere with normal activities
 - severe: prevents normal activities
- its relationship to the study treatment
 - Yes
 - No
- its duration (start and end dates) or if the event is ongoing an outcome of not recovered/not resolved must be reported.
- whether it constitutes a serious adverse event (SAE - See [Section 7.2](#) for definition of SAE) and which seriousness criteria have been met.
- action taken regarding investigational treatment

All adverse events must be treated appropriately. Treatment may include one or more of the following:

- no action taken (e.g. further observation only)
- investigational treatment dosage increased/reduced
- investigational treatment interrupted/withdrawn
- concomitant medication or non-drug therapy given
- non-drug therapy given
- patient hospitalized/patient's hospitalization prolonged (see [Section 7.2](#) for definition of an SAE)
- its outcome (not recovered/not resolved; recovered/resolved; recovering/resolving, recovered/resolved with sequelae; fatal; or unknown)

Once an adverse event is detected, it must be followed until its resolution or until it is judged to be permanent, and assessment must be made at each visit (or more frequently, if necessary) of any changes in severity, the suspected relationship to the study drug, the interventions required to treat it, and the outcome.

Information about common side effects already known about the investigational drug can be found in the investigator brochure (IB). This information will be included in the patient informed consent and should be discussed with the patient during the study as needed. Any new information regarding the safety profile of the medicinal product that is identified between IB updates will be communicated as appropriate, for example, via an investigator notification (IN) or an Aggregate Safety Finding. New information might require an update to the informed consent and has then to be discussed with the patient.

The investigator must also instruct each patient to report any new adverse event (beyond the protocol observation period) that the patient, or the patient's personal physician, believes might reasonably be related to study treatment. This information must be recorded in the

investigator's source documents; however, if the AE meets the criteria of an SAE, it must be reported to Novartis.

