The screening period allows for assessment of patient entry criteria and for patients to become familiar with spirometry measurement and daily eDiary entry prior to the collection of baseline values.

Patients experiencing an asthma exacerbation during the screening period must be designated as a screening failure. Patients who experience an asthma exacerbation during screening may be re-screened 4 weeks after complete recovery from the exacerbation.

Re-screening of patients is permitted once during the screening period.

Placebo run-in

The placebo run-in period allows for the determination of level of asthma control based on [REDACTED], FEV1 reversibility as determined by the central reader at the spirometry vendor, SABA use, and daytime asthma symptom scores for eligibility for randomization into the 12-week active treatment period. This period also allows for the collection of baseline data for all efficacy variables. During this period, patients will become familiar with administration of investigational treatment and patient's compliance with an Electronic Peak Flow/ eDiary device will be assessed.

Patients experiencing an asthma exacerbation during the placebo run-in period must be designated as a run-in failure.

Treatment period

During this period, oral QAW039 150 mg or matching placebo (1:1) will be administered once daily for 12 weeks added to SoC asthma therapy (as defined in inclusion criterion 4), with the last dose given at Week 12 and final assessment for the treatment period at Week 12. The 12-week treatment duration is considered sufficient to demonstrate an effect of QAW039 on the primary endpoint, pre-dose FEV1, in this Phase 3 study since QAW039 has previously demonstrated significant effects on pre-dose FEV1 in 12-week Phase 2 studies.

Follow-up period

The 4-week wash out period will monitor the safety and tolerability profile after the last dose of study drug.

The investigator must provide appropriate advice on the continued use of effective contraception for at least one week (at least 5 half-lives of QAW039) after the last dose of study drug and follow up with the subject as appropriate.

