5.6 Study completion and discontinuation

5.6.1 Study completion and post-study treatment

Study completion for a patient will occur after he/she has completed 12 weeks of treatment (through to Visit 299) or has prematurely withdrawn. Completion of the study will be when

all randomized patients have completed 12 weeks of treatment and the post-treatment Follow-up visit.

Patients who have been screened when enrolment target has been met will be allowed to proceed onto study participation.

A Safety Study of QAW039 is planned. At sites participating in the Safety Study, patients who successfully complete 12 weeks of treatment in this study (Study A2317) may be offered participation in the Safety Study; patient participation in the Safety Study will be optional. Patients not entering the Safety study will complete the follow-up period and will not be given further access to study drug because the risk/benefit ratio will not yet have been substantiated and there are already other marketed therapeutic alternatives available to treat these patients. At the time of study completion or early termination, all patients will be placed on the appropriate asthma treatment as prescribed by the investigator.

The investigator must provide appropriate advice on the continued use of effective contraception for at least one week (at least 5 half-lives of QAW039) after the study completion visit (Visit 299) or premature study drug discontinuation and must follow up with the subject as appropriate at least to the end of this period.

The investigator must provide follow-up medical care for all patients who are prematurely withdrawn from the study, or must refer them for appropriate ongoing care.

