Medical History – Protocol solicited events for asthma	X										
Asthma exacerbation history	X										
Smoking history	X										
Prior/concomitant medication (asthma and non-asthma medications) review	X		X		X	X	X	X	X		
Inclusion/exclusion criteria	X		X								
Review and record surgeries and procedures	X		X		X	X	X	X	X		
Physical examination	S							S	S		
Abbreviated physical examination			S		S	S	S				Heart and lungs only.
ACQ-5 in clinic			X								
AQLQ+12 in clinic			X			X		X	X		

[figure not shown]
Period	Screen	Placebo Run-in		Treatment						Follow-up	Notes
Visit Number (Site visits)	1	101	199	201	202	203	204	TD	299	301	Follow-up Visit 301 is only applicable for patients not participating in the safety study.
Treatment Week	-3	-1	0	0	2	4	8	TD	12	16	Visit 199 and Visit 201 occur on the same day.
Treatment Day	-21	-7	1	1	14	28	56		84	112	
Train patient and assess patient's ability to use eDiary/ePEF and dispense eDiary/ePEF	S										
Review eDiary /ePEF compliance		S	S [†]								† eDiary/ePEF compliance must be assessed prior to randomizing the patient.
Review eDiary/ePEF entries		S	S		S	S	S	S	S		
Height	X							X	X		
Weight	X		X					X	X		
Vital signs	X	X	X		X	X	X	X	X		Systolic/diastolic blood pressure, radial pulse (sitting), and body temperature.
Electrocardiogram	X							X			
Electrocardiogram (Pre-dose)				X					X		
Pregnancy test—serum (women of child bearing potential)	X										Pregnancy testing will begin at the visit a patient is first identified as being of child bearing potential. If positive, the patient must not be randomized.
Pregnancy test—urine dipstick test in clinic (women of child bearing potential)			X			X	X	X	X	X	Pregnancy testing will begin at the visit a patient is first identified as being of child bearing potential. A positive urine pregnancy test requires immediate interruption of study drug until serum β-hCG is performed and found to be

Period	Screen	Placebo Run-in		Treatment						Follow-up	Notes
Visit Number (Site visits)	1	101	199	201	202	203	204	TD	299	301	Follow-up Visit 301 is only applicable for patients not participating in the safety study.
Treatment Week	-3	-1	0	0	2	4	8	TD	12	16	Visit 199 and Visit 201 occur on the same day.
Treatment Day	-21	-7	1	1	14	28	56		84	112	
											negative. If positive, the patient must be discontinued from study drug.
Urinalysis and urine chemistry (central laboratory)	X			X				X	X		

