Blood sample for hematology and chemistry (central laboratory)	X			X				X	X		No fasting requirement prior to blood sampling.
Blood sample for RAST/ImmunoCAP test (central laboratory)	X										
Review Visit 1 laboratory results		S									If results for chemistry, hematology, HbA1c, RAST/ImmunoCAP, urine chemistry and urinalysis are missing, obtain a repeat for the missing result.
Parasitic screening	S										Only if required by health authority and/or ethics committee/ institutional review board. Sites should use local laboratories.
Spirometry (centralized)	X							X			
1 st Pre-dose Spirometry (centralized) approximately - 45 min. pre-dose		X		X	X	X	X		X		To be performed approximately 45 min. prior to in-clinic witnessed study drug administration.
2 nd pre-dose Spirometry (centralized) approximately -15 min. pre-dose		X ^ε		X	X	X	X		X		To be performed approximately 15 min. prior to in-clinic witnessed study drug administration.

Period	Screen	Placebo Run-in		Treatment						Follow-up	Notes
Visit Number (Site visits)	1	101	199	201	202	203	204	TD	299	301	Follow-up Visit 301 is only applicable for patients not participating in the safety study.
Treatment Week	-3	-1	0	0	2	4	8	TD	12	16	Visit 199 and Visit 201 occur on the same day.
Treatment Day	-21	-7	1	1	14	28	56		84	112	
											£To be performed prior to reversibility test.
Reversibility test (spirometry after administration of short-acting β -agonist [SABA])	X**	X ^{α,β**}									
¤To be performed prior to in-clinic witnessed study drug administration.
 
£To be performed after the second (-15 min.) pre-dose spirometry (may be performed after 10 AM \pm 1 h).
 
**If reversibility is NOT demonstrated at Visit 1, reversibility will be attempted at Visit 101. If not achieved, then one additional attempt allowed within 4 days following Visit 101.

Review Visit 1 or Visit 101 or the one additional attempt reversibility result from overread			S								
Asthma exacerbation monitoring	X	X	X	X	X	X	X	X	X	X	In case of an asthma exacerbation, the patient should be encouraged by the site to contact it for advice. If necessary, an unscheduled visit to the site may be arranged.
Serious adverse event monitoring	X	X	X	X	X	X	X	X	X	X	
Adverse event monitoring	X	X	X	X	X	X	X	X	X		
Liver event monitoring	X	X	X	X	X	X	X	X	X	X	If applicable, review lab results and clinical events as per Section 7.3 .
Renal event monitoring	X			X				X	X		If applicable, review lab results as per Section 7.4 .

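### Table 6-1 schedules no general adverse event enquiry at follow-up Visit 301, although Protocol 7.1 requires one at every study visit

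*Protocol*

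**What the plan says.** Protocol 7.1 sets the enquiry rule: "The occurrence of adverse events must be sought by non-directive questioning of the patient at each visit during the study". It counts adverse events from consent "for participation in the study until the end of study visit", but no section says which visit that is.

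Protocol 3.1 lists the 4-week follow-up as one of the periods of the study. The follow-up paragraph of the design rationale in Protocol section 3 gives its purpose: "The 4-week wash out period will monitor the safety and tolerability profile after the last dose of study drug".

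In Table 6-1 the general "adverse event monitoring" row is marked at every visit up to Visit 299 and is empty at Visit 301. The rows for serious adverse events, asthma exacerbations, liver events and deaths are marked at Visit 301. Visit 301 applies only to patients who do not enter the safety study.

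Three places deal with when an event counts as treatment-emergent:

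- Protocol 9.5.2.1 starts at the first intake and gives no end.
- SAP 2.7.1 ends at 7 days after the last intake (30 days for serious events). It leaves out events after Visit 299 in patients who go straight into the safety study.
- SAP section 4 describes the protocol's definition as ending the day after the last intake.

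**The concern.** Safety is a secondary objective, and follow-up exists to observe patients after the last dose. A site that works from Table 6-1 would not ask about new non-serious events at Visit 301. A site that works from Section 7.1 would. Collection could then differ between sites, and in an interval whose events the analysis counts as treatment-emergent. A low count of non-serious events after Day 84 could not be told apart from a lack of asking.

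**Working it through.** **1. The table.** Table 6-1 has ten visit columns: 1, 101, 199, 201, 202, 203, 204, TD, 299 and 301.

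| Row | Visits marked | Visit 299 | Visit 301 |
|---|---|---|---|
| Serious adverse events | 10 of 10 | X | X |
| Adverse events (general) | 9 of 10 | X | empty |
| Asthma exacerbations | 10 of 10 | X | X |
| Liver events | 10 of 10 | X | X |
| Deaths | 10 of 10 | X | X |

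The serious and general rows each have 11 cells (ten visits plus notes), so the blank is not a shifted column.

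**2. The interval.** The last dose for completers is at Week 12 (Visit 299, Day 84), and Visit 301 is Day 112: 112 − 84 = 28 days, Days 85 to 112. Protocol section 6 puts the safety assessments before the in-clinic dose, so the last scheduled general enquiry comes before the last dose.

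**3. Overlap with the analysis.** The SAP window for non-serious events ends on Day 84 + 7 = Day 91. Days 85 to 91 are 7 of 91 days, or 7.7%. Under Protocol 9.5.2.1 all 28 days count.

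**4. Who is affected.** Patients who stop treatment early are asked to keep attending through Visit 299, where the row is marked. For those who fail to return, Protocol section 6 provides a phone contact, if they agree to it, that covers adverse events. Patients who enter the safety study are outside the window by SAP 2.7.1. That leaves completers who do not enter it. With the planned 15% discontinuation, completers number 650 × 0.85 = 552.5. The documents do not state the share entering the safety study. At assumed shares of 0%, 50% and 90%, about 552, 276 and 55 patients are affected.

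**5. Illustration of size.** Assume a constant event rate, and let p be the probability of at least one non-serious event in 84 days. The probability that a first event falls in the next 7 days is (1 − p) × (1 − (1 − p)^(7/84)):

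- p = 0.2: 1.47 percentage points
- p = 0.4: 2.50
- p = 0.6: 2.94, which is also the maximum to two decimals (reached at p = 0.617)

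Per arm, 2.94 × 0.85 × (1 − share entering the safety study) gives 2.50, 1.25 and 0.25 points at shares of 0%, 50% and 90%. These figures describe events not actively sought. Some of those events would be recorded anyway.

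**The case against.** The best defence is that a patient's study ends at Visit 299. Protocol 5.6.1 says that a patient completes the study through that visit, and it sets the contraception period to run "after the study completion visit (Visit 299) or premature study drug discontinuation". Both the adverse event period and the rule on visits could then stop there, and Table 6-1 would agree.

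The reading is possible but does not remove the conflict. Protocol 3.1 makes follow-up part of the study, its stated purpose is safety after the last dose, and 5.6.1 itself defines completion of the trial as the point when "all randomized patients have completed 12 weeks of treatment and the post-treatment Follow-up visit". If the period did end at Visit 299, the SAP's 7-day window would run past it. Section 7.1 sends new, possibly related events after the observation period only to source documents unless they are serious.

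Several points on the other side stand, and they limit what a reader may infer:

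- **That no non-serious event is looked for after the last dose.** This goes too far. Exacerbation and liver event monitoring at Visit 301 can find non-serious events; a moderate exacerbation need not be serious. Section 7.1 also allows for unprompted reports: "Adverse events also may be detected when they are volunteered by the patient during or between visits". Known events must be reassessed at each visit. Only the general enquiry is missing.
- **That the SAP widened the window from one day to seven.** That follows SAP section 4, but the current Protocol 9.5.2.1 has no end date. Against that text the SAP narrows the window.
- **That 2.94 points is a ceiling.** It is one only under a constant rate. Events clustered after stopping drug could exceed it.
- **That the blank "Prior/concomitant medication (asthma and non-asthma medications) review" cell at Visit 301 is a second gap.** Protocol 5.5.7 already requires patients to report new medications and sites to record all of them after enrollment. Marking the cell would be tidy but is optional.

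**Conclusion.** The point holds as a minor inconsistency in data collection. Table 6-1 omits a general enquiry that Section 7.1, read with Section 3.1 and the purpose of follow-up, calls for. For completers outside the safety study this leaves 28 days without it, 7 of them inside the SAP window. The loss should be small, because other routes catch some events, and similar in both arms, because the schedule and the blinding are common to both. The number of events missed cannot be fixed from the documents: it depends on the event rate after stopping, the share entering the safety study and how many events are volunteered, none of which is given.

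A reader might infer a bias between arms or a weakness in the efficacy results. The documents support neither. Scheduled collection of serious events, exacerbations, liver events and deaths at Visit 301 is intact, and efficacy, power and type I error are untouched. The end of the treatment-emergent period is a separate, related mismatch among Protocol 9.5.2.1, SAP 2.7.1 and SAP section 4.

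**What to change.** - Mark general adverse event monitoring at Visit 301 in Table 6-1, so that it agrees with Protocol 7.1.
- State in Protocol 7.1 which visit is the end of study visit.
- Give one end date for treatment-emergent events in Protocol 9.5.2.1 and SAP 2.7.1, and make the description in SAP section 4 match the protocol text.

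The cost is one table cell, one definition, an aligned sentence in each document, and a few more entries at a visit that already takes place. If those visits have already happened, the report should say that no general enquiry about non-serious events was scheduled after the last dose for completers outside the safety study. That costs one sentence. A supplementary table of events cut at the last dose is optional.
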